**EXCLUSION CRITERIA:**

- 1) Is greater than 6 months of age
- 2) Has not been diagnosed with TSC
- 3) History of seizures or infantile spasms, or evidence of subclinical electrographic seizures on a previous video EEG
- 4) Has received any anticonvulsant medication including vigabatrin, other anti-seizure therapeutic agent including cannabidiol
- 5) Has received an oral mTOR inhibitor such as everolimus or sirolimus
- 6) Has taken an investigational drug, including but not limited to cannabidiol, as part of a research study 30 days prior to enrollment, or plans on taking an investigational drug at any time during the duration of the study
- 7) Is currently enrolled, or plans on enrolling at any time during the duration of the study, in an experimental behavioral early intervention study
- 8) Has a history of being born prematurely (born less than <30 weeks gestation at the time of delivery)

Subjects who have consented and at the time of their baseline study visit and show evidence of electrographic seizures on their initial video EEG will exit from the PREVeNT study and proceed with initiation of management of their clinical condition. All other enrolled subjects will be followed until the age of 36 months with physical and neurologic exams, serial 1-hour awake and sleep video-EEGs, and ophthalmologic evaluation at baseline and defined intervals, every 6-12 weeks based on subjects chronological age.

Study visits and procedures are based on subjects' chronological age in months ( $\pm$ 1 week if under 12 months of age and  $\pm$ 2 weeks if 12 months and older). Once enrolled, subjects enter a 'watchful waiting' protocol which includes baseline EEG at 1.5 month (~6 week) intervals until 12 months of age, then every 3 month (~12 week) intervals until 24 months of age. Subjects will continue in this protocol phase until treatment is justified.

Randomization will be stratified into two groups, according to age at time of emergence of EEG biomarkers: 1)  $\leq$  7 months; 2)  $>$ 7 months of age. This is to account for natural history studies and data from our P20-NS080199 study that indicates mean age of clinical seizure onset less than 7 months of age, with a significant portion of TSC infants developing seizures between 6-12 months and still others after 12 months of age. Accordingly, this randomization strategy will ensure we are able to evaluate age independently of timing of EEG change and treatment randomization.

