For the accurate identification of clinical seizures, parents and caregivers will review a seizure recognition video at the time of study enrollment and retain it as a reference throughout the study. They will also be encouraged to video any suspicious events during the study period for review by clinicians of the investigation team. If at any point during the study the subject is suspected of having a clinical seizure, the parents/caregiver will be instructed to contact their site's study coordinator. The subject will be seen as soon as possible for a study visit and a video EEG will be completed for confirmation of clinical or electrographic seizure onset. Those subjects with either a documented clinical seizure on video or evidence of an electrographic seizure on video EEG will be transitioned to the Open-Label treatment phase.

At the emergence of abnormal epileptiform activity (*i.e.* sharp waves, spikes or polyspikes, spike and wave discharges, classic or modified hypsarrhythmia) prior to the onset of the first clinical or electrographic seizure, subjects will enter the protocol blinded-treatment phase (Arm A). Emergence of these specific, predetermined EEG biomarkers detected by video EEG will lead to a 1:1 randomization with vigabatrin or placebo. The vigabatrin and placebo will be dispensed as a sachet and those subjects randomized to vigabatrin will be titrated up to 100mg/kg/day by 50mg/kg/day every 3 days during the blinded phase of the study. The research pharmacist at each site will be unblinded during this phase of the study and the vigabatrin and placebo sachets doses will be identical in order to maintain the blind.

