If an enrolled subject has an electrographic or clinical seizure(s) prior to randomization and the previous EEG(s) have been normal they will move into the Open label phase of the study (Arm B). If the seizures are not controlled in the Open label phase at the vigabatrin maximum dose of 150mg/kg/day, the investigator may change the antiepileptic medication as clinically warranted to improve seizure control (including tapering off vigabatrin). These subjects will remain in the open arm of the study for the duration of the protocol (36 months).

Patients enrolled without prior clinical seizures but found on first baseline EEG to have electrographic or clinical seizures of which the parent and clinician were previously unaware will exit the PREVeNT trial and begin medical treatment by the site PI based on clinically accepted management guidelines for seizures in TSC infants. Based on the P20-NS080199 study, this group is estimated to be very small (<5%) and will not affect the total number of enrolled patients (N=80) eligible to be randomized to either placebo or vigabatrin treatment.

Enrolled subjects who never develop EEG abnormalities or clinical seizures (ARM C) will remain in the study and continue with regular clinical evaluations, EEG testing, and developmental assessments as scheduled (Table 2). Without EEG change or developing seizures, they will have neither been randomized nor treated with vigabatrin. These patients will serve as a negative control and be key for validating the sensitivity and specificity of EEG biomarkers as predictors of seizure risk and baseline disease characteristics attributable to TSC that are independent of epilepsy and AED treatment (TREATMENT ARM A).

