Additional developmental measures and ASD Risk: The sub-scores on the Bayley-III and the composite score estimated using Hotelling’s  $T^2$ . The power for this endpoint will vary, but is expected to be similar to the primary. In the children with Pervasive Developmental Disorders, the effect sizes versus normal matched controls were 1.77, 1.67, 1.17 and 1.33 for the Receptive communication, Expressive Communication, Fine and gross motor sub-scores respectively. The ADOS2 will be completed at 24 and 36 months of age as a neurodevelopmental assessment for symptoms of ASD. The results from Study Arm A (seizure free, no treatment), Arm B (VGB versus. Placebo), and subjects with electrographic seizures at baseline EEG who move directly into Open Label treatment will be compared increasing our power to assess differences (Figure1).

Determination of vigabatrin safety as a preventative treatment for clinical seizures in infants with TSC will be assessed using comparison between the treatment groups and as a summary of exposure time on the drug. The outcome measure will be percentage of patients in each group (vigabatrin early treatment vs. vigabatrin delayed treatment) with treatment associated adverse events (AEs), serious adverse events (SAEs), and risk evaluation and mitigation strategy (REMS) measures. Treatment related AEs and SAEs will be monitored and tabulated. Given the expectation that the delayed group will cross-over to active treatment sooner than the early treatment group, adverse events will be characterized using life table approaches to ensure adjustment for exposure time. Thus, counts of individuals with AEs, total number of specific AEs and rate per months of follow-up will all be provided and assessed for any differences and for the safety population (early plus late on person years of exposure basis). Events of specific interest and risk evaluation and mitigation strategy (REMS) measures will be compared, including any and all ophthalmologic problems that may arise. Data from the negative control group (estimated to be approximately 15-20 patients) will also be used to compare the occurrence of AEs and SAEs.

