Additional measures and analyses considerations: We will use descriptive statistics to quantify the percentage of patients requiring unblinded treatment after randomization and the duration of blinded treatment within the study period. We will also determine the percentage of randomized patients at 24 and 36 months of age with drug-resistant epilepsy as a clinically meaningful and significant correlate to the time to first seizure measure. As noted above, Cox regression models will be attempted with the pre-treatment covariates from the baseline and index EEG (that is, the biomarker findings that initiated the randomization) to examine if there are gradients in the predictors and levels of risk/time to events that can be predicted. These analyses will be done both within the treatment group and with the interaction of treatment and biomarkers included in the model. Since subject randomization is based on EEG findings, not seizure onset and the most common age of seizure onset is 3-7 months based on published natural history studies and the data from our P20-NS080199 study. The subjects will be stratified into two groups for the analysis: 1) subjects randomized based on EEG biomarkers <12months, 2) subjects randomized based on EEG biomarker >12 months of age. There will be 2 additional groups in the analysis: subjects with normal EEGs, seizure free and never randomized and subjects with electrographic seizures at baseline, never randomized but treated with vigabatrin (the 28-30 children not randomized). Additional analysis will be done to measure the impact of concomitant AEDs used during the study.

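### The autism-risk and additional-group analyses list children who exit at baseline, give no group to never-randomised Arm B children, and credit non-randomised groups with added power

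*Combined protocol and SAP*

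**What the plan says.** All places are in the combined protocol and SAP.

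**Analysis text.** Under Analyses, the paragraph on additional developmental measures and ASD risk names three sets of children for the ADOS-2 comparison at 24 and 36 months. It begins "The results from Study Arm A (seizure free, no treatment), Arm B (VGB versus. Placebo" and then adds that "subjects with electrographic seizures at baseline EEG who move directly into Open Label treatment will be compared increasing our power to assess differences". The paragraph on additional measures and analysis considerations adds two groups to the randomised strata: never-randomised children with normal EEGs and no seizures, and "subjects with electrographic seizures at baseline, never randomized but treated with vigabatrin". It puts the non-randomised children at 28-30.

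**Protocol body.** The text after the exclusion criteria defines the arms differently:

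- Arm A is the randomised phase: when epileptiform activity appears, "subjects will enter the protocol blinded-treatment phase (Arm A").
- Arm B is open label. Of children whose first seizure comes before randomisation and after normal EEGs, it says "they will move into the Open label phase of the study (Arm B"). On follow-up it says "These subjects will remain in the open arm of the study for the duration of the protocol (36 months"). The section on vigabatrin and placebo also moves randomised children who have a seizure on study drug into Arm B.
- Arm C is the untreated group: "Enrolled subjects who never develop EEG abnormalities or clinical seizures (ARM C) will remain in the study".
- Children with "evidence of electrographic seizures on their initial video EEG will exit from the PREVeNT study". The same rule appears twice more in the body, which estimates this group at under 5%.

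**The concern.** Four things do not fit together.

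1. A group that leaves at baseline is listed for comparison on instruments given at 24 and 36 months.
2. A never-randomised group that the body keeps to 36 months has no place in either analysis paragraph.
3. The autism paragraph calls the body's Arm C Arm A, and the body's Arm A Arm B. The body's Arm B mixes never-randomised children with randomised children who later had a seizure. An analyst who selected Arm B by the body's definition would therefore be selecting partly on a post-randomisation outcome.
4. Extra power is claimed from groups that were not randomised and are defined by their EEG and seizure course. Differences from those groups reflect disease severity as well as any treatment.

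At stake is how the autism-risk part of secondary objective 2, and the additional group analyses, are carried out and read.

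**Working it through.** **1. The groups side by side**

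| Children | Protocol body | Autism-risk paragraph | Additional-analyses paragraph |
|---|---|---|---|
| Randomised to vigabatrin or placebo | Arm A | called Arm B | strata by age at biomarker, no arm letter |
| Normal EEG, seizure free, untreated | Arm C, followed | called Arm A | a group, no arm letter |
| Seizure on baseline EEG | exit (three statements) | a group, said to go to open label | a group, said to be treated with vigabatrin |
| First seizure before randomisation, after normal EEGs | Arm B, to 36 months | no group | no group |

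The label error is in the autism paragraph only. It is a shift (C becomes A, A becomes B), and the true open-label Arm B is left without a label.

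**2. How many children have no group**

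The plan gives no number, so I take the remainder: enrolled, minus biomarker positive, minus Arm C. Inputs:

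- 80 enrolled.
- 62.5% biomarker positive (recruitment monitoring and sample size text), or 75% (EEG biomarker feasibility; read here as a share of those enrolled, which is an assumption).
- Arm C of 24 (vigabatrin and placebo section), or a negative control group of 15-20 (safety text under Analyses).

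The plan's own count reproduces: 0.375 × 75 = 28.1 and 0.375 × 80 = 30, so 28-30 are not randomised.

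- 62.5% positive: 80 − 50 − 24 = 6; 80 − 50 − 20 = 10; 80 − 50 − 15 = 15.
- 75% positive: 80 − 60 − 20 = 0; 80 − 60 − 15 = 5; 80 − 60 − 24 = −4, which is impossible.

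The feasible range is 0 to 15. If the exit group is counted within the 80, it takes up fewer than 0.05 × 80 = 4 of the remainder. The figures also conflict elsewhere: the sample size text calls all 28-30 biomarker free, while the additional-analyses paragraph divides them between normal-EEG and baseline-seizure children.

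A separate illustration uses the pilot sensitivity of 73.7%. If 62.5% of 80 have seizures, 50 × (1 − 0.737) = 13.2 would have no prior biomarker; for 75 enrolled, 46.9 × 0.263 = 12.3.

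**3. What the added groups do for power**

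The autism paragraph gives no power figure of its own, so the primary endpoint's inputs stand in: 24 per arm, effect size 0.885, two-sided 0.05.

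- Plan's figure: noncentrality 0.885 × √(24/2) = 3.07 on 46 degrees of freedom gives 85.1%, matching the stated 85%.
- Add 15-30 non-randomised children to the same model, assuming a common SD. The vigabatrin-placebo contrast and its two arm sizes do not change; only the error degrees of freedom rise, to 46 + 15 − 1 = 60 (one added group) or 46 + 30 − 2 = 74 (two). Power becomes 85.5% to 85.7%, a gain of 0.3 to 0.6 points.
- Test all groups jointly, assuming the non-randomised means lie midway between the two arms. Omnibus F power is about 77% with three groups and about 71% with four.
- Bonferroni over three or six pairs gives about 73% or 64% for the vigabatrin-placebo pair.

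If Arm C lay well away from both randomised arms, the joint test would reject more often, but because it detected a difference in disease course.

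**The case against.** The strongest reply is that the first two faults are one slip. Children who go straight to open label, unrandomised and on vigabatrin, match the body's never-randomised Arm B entrants and do not match children who exit. On that reading only the reference to baseline is wrong. The EEG biomarker feasibility paragraph also expects seizures before the biomarker, so these children are not absent from the plan as a whole. This is plausible and may be what was meant. It does not remove the conflict, because both analysis paragraphs say baseline and the body says three times that those children exit.

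Four stronger readings that a reader might infer do not stand:

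- **The autism analysis cannot be run.** The randomised and the seizure-free untreated groups are described in words, can be identified and are followed. Only the third group has no scheduled data.
- **The arms are mislabelled throughout the analysis plan.** The shift is in one sentence; the additional-analyses paragraph uses no arm letters.
- **About 13 children are left out.** That is one point near the top of the range. It treats 62.5% as a seizure rate although the plan also uses it as the biomarker-positive share, and the pilot sensitivity came from an analysis focused on ages 6 to 24 months, whereas this trial enrols at or below 6 months.
- **The sponsor plans to present a treated-versus-untreated difference as a better-powered treatment effect.** The power statement does not say which differences it means, and the body gives Arm C the role of negative control. The wording leaves room for that misreading but does not plan it.

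**Conclusion.** The point holds as an inconsistency in the analysis text that should be corrected. As written, one listed group has no scheduled 24- or 36-month data under the exit rule, and one followed group, of about 0 to 15 of 80 children, has no place in either analysis paragraph. One sentence shifts the arm labels. The power statement is unsupported: the gain for the randomised contrast is 0.3 to 0.6 points under a common SD, and a joint or multiplicity-adjusted comparison lowers power under the assumptions shown.

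The count rests on the plan's own conflicting shares. The power figures rest on the cognitive endpoint's inputs, since none are given for the ADOS-2. Only secondary and exploratory analyses are touched; the primary cognitive comparison, randomisation and sample size are not.

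**What to change.** In the ASD-risk paragraph, use the body's arm labels. State that the treatment comparison is randomised Arm A, vigabatrin versus placebo, which matches the early-versus-late contrast in secondary objective 2. Delete the statement about increased power.

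In both analysis paragraphs, report never-randomised Arm B children and Arm C children as separate, descriptive, non-randomised groups, and state the expected size of each from one consistent set of figures.

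Reconcile the baseline-seizure group with the three exit statements, so that the document says one thing about whether these children are followed and analysed. How they are managed is for the sponsor and is not addressed here.

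The cost is wording in two paragraphs, best settled before unblinding; no new data are needed. What is lost is a nominally larger comparison that was confounded by disease course.

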### **Secondary Study Objectives:**

- 1) Determine the effectiveness of early versus delayed treatment with vigabatrin in clinical seizure prevention. The outcome measure will be time to first clinical seizure following randomization. The prevalence of drug-resistant epilepsy will be assessed at 24 months for each group (vigabatrin early treatment vs. vigabatrin delayed treatment).
- 2) Determine the impact of early versus late treatment on the other components of the Bayley-III (receptive communication, expressive communication, fine and gross motor skills) and risk of autism spectrum disorders (ASD). The primary outcome measures for this objective will be subdomain scores of the Bayley-III, Vineland-II (Survey Interview Form), Beery Visual Motor Integration (VMI), and ADOS2 at 24 months. Additional exploratory analysis will be completed at 36 months to assess changes observed at 24 months are consistent with those seen at 36 months and indicative of long-term outcome. At 36 months of age subjects will also complete the Peabody Picture Vocabulary Test (PPVT). During the COVID-19 Pandemic in order to minimize the risk of infection to observer and infant until the completion of the study the Brief Observation of Symptoms of Autism (BOSA) will be administered at 24- and 36-month visits. Additionally, the ADI-R will be administered at the 36-month visit.
- 3) Confirm vigabatrin safety as a preventative treatment for clinical seizures in infants with TSC. The outcome measure will be percentage of patients in each group (vigabatrin early treatment vs. vigabatrin delayed treatment) with treatment associated adverse events (AEs), serious adverse events (SAEs), and risk evaluation and mitigation strategy (REMS) measures.
- 4) Confirm of the feasibility of using EEG biomarkers to identify TSC infants at risk for developing epilepsy. The outcome measure will be the sensitivity and specificity of EEG epileptiform activity in predicting epilepsy outcomes at 24 months within treatment groups.

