To further maintain the treatment blind, subjects who experience their first seizure after randomization to either vigabatrin or placebo will follow the same blinded 2 week transition to open label vigabatrin (dose increased to 150mg/kg/day in the open label phase), so that all patients regardless of randomization group will exit the blinded treatment phase in identical fashion. This way, neither the treating physician nor the parent/guardian would know which treatment group the child had been assigned. Only the PREVeNT trial independent medical monitor and research pharmacists at each site would have access to randomization assignments throughout the study. The blinded 2 week transition phase will also occur if the subjects in Arm A are seizure free at the time of their 24 month of age study visit. They will be tapered off the study drug (vigabatrin or placebo) without breaking the treatment blind and continue to be followed for the duration of the study (36 months) under best medical care (*i.e.* if seizures develop, vigabatrin may be initiated).

Both vigabatrin and placebo will be repackaged into identical aluminum foil sachets so as to maintain treatment blinding and distribute as appropriate to the investigational pharmacies at local participating sites for individual patient distribution and administration. For administration, the entire content of one sachet (500 mg active drug) is dissolved in 10 ml water for oral administration that is dosed according to body weight 50-150 mg/kg/day divided BID. Dosing will follow established recommended guidelines (50 mg/kg/day and increased as needed by 50 mg/kg/day every 3 days up to 100mg/kg/day during the blinded phase of the study, divided BID).

Only those subjects who have clinical seizures or electrographic seizures in the blinded treatment phase of the study will transition to open label vigabatrin to a dose of 150mg/kg/day.

Note\*\* Subjects who have consented and at the time of their baseline study visit and show evidence of electrographic and/or clinical seizure(s) on their initial video EEG will exit from the PREVeNT study and proceed with initiation of management of their clinical condition.

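### The named safety measure compares early with delayed vigabatrin, with no blinded-phase window or dose split, so it dilutes any adverse-event difference due to preventive treatment

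*Combined protocol and SAP*

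**What the plan says.** Secondary Study Objectives, item 3, sets the aim: "Confirm vigabatrin safety as a preventative treatment for clinical seizures in infants with TSC". The measure attached to it is repeated in the safety paragraph under Analyses: "The outcome measure will be percentage of patients in each group (vigabatrin early treatment vs. vigabatrin delayed treatment) with treatment associated adverse events (AEs", with SAEs and REMS measures alongside. Neither place gives an observation window.

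The safety paragraph does more than report percentages. It recognises that the delayed group will cross to active drug and states that "adverse events will be characterized using life table approaches to ensure adjustment for exposure time". It adds that "counts of individuals with AEs, total number of specific AEs and rate per months of follow-up will all be provided" to look for differences. A further summary is made "for the safety population (early plus late on person years of exposure basis". It also brings in an untreated comparator: "Data from the negative control group (estimated to be approximately 15-20 patients) will also be used" to compare AEs and SAEs. Separately, the Protocol description says that all seizure treatments and dosing will be recorded and analysed for several purposes, one of which is safety. It gives no method for this.

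On exposure, the Protocol description sets blinded vigabatrin at up to 100 mg/kg/day. Children in either randomised group who have a seizure follow a "blinded 2 week transition to open label vigabatrin (dose increased to 150mg/kg/day in the open label phase". Elsewhere in the same section 150 mg/kg/day is called a target, and the clinician may adjust vigabatrin as tolerated, add treatment or switch.

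**The concern.** The objective is about giving vigabatrin before any seizure, to infants whom the background section describes as otherwise asymptomatic. The trial's randomised information on that question comes from the blinded phase, when one group takes vigabatrin and the other placebo. Once placebo children cross over, their vigabatrin-related events count in the delayed column. The measure then largely compares vigabatrin with later vigabatrin, aimed at a dose 150/100 = 1.5 times as high.

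The trial is meant to supply evidence for a Phase III study. A small gap between early and delayed percentages would say little about the harm of preventive treatment, yet it is the result attached to the safety objective.

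**Working it through.** **Inputs from the documents.** 24 per arm, with seizure proportions of 22/24 = 0.917 on placebo and 5/24 = 0.208 on vigabatrin (Statistical Methods, Primary Study Objective). Stated doses as above. Expected time on vigabatrin is slightly under 1-2 years (delayed) and 2-3 years (early) (Analyses).

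**The plan's own figure.** The seizure proportions come from the power statement. Exact enumeration of Fisher's two-sided test at 0.05 gives power 0.9998 for 0.917 versus 0.208 (stated: 99%) and 0.963 for 0.917 versus 0.417 (stated: above 90%). Both agree with the plan. No power is stated for safety.

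**Dilution model.** The documents give no overall AE risks, so these are assumptions:
- b = background AE risk, equal in both groups
- r = risk due to vigabatrin in the blinded phase
- q = m × r = risk due to vigabatrin in the open-label phase

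Blinded phase only:
- early = 1 − (1−b)(1−r)
- delayed = b
- difference = (1−b)r

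All follow-up:
- early = 1 − (1−b)(1−r)(1 − (5/24)q)
- delayed = 1 − (1−b)(1 − (22/24)q)

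Dividing the second difference by the first, b cancels:

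share kept = 1 − m × [22/24 − (5/24)(1−r)]

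| m | r = 0.20 | r = 0.50 |
|---|---|---|
| 0.5 | 1 − 0.5 × 0.750 = 62.5% | 1 − 0.5 × 0.8125 = 59.4% |
| 1.0 | 1 − 0.750 = 25.0% | 1 − 0.8125 = 18.8% |
| 1.5 | 1 − 1.125 = −12.5% | 1 − 1.219 = −21.9% |

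The sign changes at m = 1/0.750 = 1.33 (r = 0.20) or 1/0.8125 = 1.23 (r = 0.50).

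**Worked case, b = 10%, r = 30%** (Fisher power at 24 per arm):
- Blinded phase: 37.0% versus 10.0%, difference 27.0 points, power 0.52.
- All follow-up, m = 0.5: 39.0% versus 22.4%, difference 16.6 points, power 0.16.
- All follow-up, m = 1: 40.9% versus 34.7%, difference 6.2 points, power 0.04.
- All follow-up, m = 1.5: 42.9% versus 47.1%, difference −4.2 points.

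**Do the additional summaries restore the contrast?**
- *Rate per month of follow-up.* The denominator includes time off drug. If drug-related events accrue evenly with time on vigabatrin, whatever the dose, the plan's durations keep (2−1)/2 = 50% to (3−2)/3 = 33% of the difference that an unexposed comparator would show.
- *Person-years of exposure.* This pools early and late children, so it contains no between-group contrast. The delayed group would supply 1/3 = 33% to 2/5 = 40% of the vigabatrin time.
- *Life tables.* These adjust for time. No censoring at crossover is stated.
- *Negative controls.* These children are not randomised and are selected for a normal EEG and no seizures. Their eye examinations are at baseline, 12, 24 and 36 months, against every three months in the blinded phase, so eye findings are not equally ascertained.
- *Dosing analysed for safety.* This is promised in general terms, with no comparison defined.

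**The case against.** The strongest reply is that the plan saw the problem. It names the crossover, adjusts for exposure time, adds rates and person-years, includes an untreated group and commits to analysing dosing for safety. Early versus delayed is also the trial's own question, so a safety table for the two strategies is legitimate. All of this stands: the fault is an unspecified comparison, and safety does not rest on percentages alone.

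Some stronger readings are tempting, and the documents do not support them:
- *That the plan defines a whole-study percentage.* It gives no window; counting all follow-up is an inference from that silence.
- *That about 92% of the signal is lost.* This follows from 22/24 only if any exposure carries the full risk regardless of dose and duration, and open-label treatment adds nothing in the early group. The plan expects different durations, and other assumptions keep far more.
- *That delayed children all receive 150 mg/kg/day.* It is a target, adjustable and followed by other options.
- *That similar percentages would be declared proof of safety.* No decision rule says so.

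The blinded contrast is not fully clean either. Blinded treatment ends at a seizure, which treatment is expected to affect (22/24 versus 5/24), so placebo time is shorter and its ending may be informative. Power is low as well: at 24 per arm Fisher's test has about 29% power for 15% versus 0% and about 9% for 10% versus 0%. These points limit what the fix can show. They do not make the diluted comparison a better answer to objective 3.

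**Conclusion.** The concern holds as a gap in specification. The measure named for objective 3 has no blinded-phase window and no split by dose, and on the plan's own seizure assumptions most of the comparator group goes on to vigabatrin. None of the supplementary summaries, as described, provides randomised vigabatrin versus placebo.

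The direction is firm across the scenarios examined: the difference shrinks or reverses in each. The size is not firm. It rests on assumed AE risks (r from 20% to 50%), on background risk being equal across phases, on ignoring unequal blinded time, and on all follow-up being counted. No view is taken on either dose. Because this is a secondary objective and the data are already being collected, it should be corrected as an analysis-plan matter; it does not call the design into question.

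**What to change.** 1. Make the main randomised safety comparison vigabatrin versus placebo during blinded treatment. Count AEs, SAEs and eye findings from first dose to the start of the two-week transition or taper. Report incidence per month of blinded treatment, and life-table estimates censored at transition.
2. Add a table of events per unit of vigabatrin-exposed time, by phase and by dose actually received, across both randomised groups. This gives content to the existing commitment to analyse dosing for safety.
3. Keep the early-versus-delayed and negative-control tables as supportive.
4. State the limits: blinded follow-up is expected to be shorter on placebo and ends at a seizure, which treatment may affect, and power at about 24 per arm is low. Report estimates with confidence intervals and do not read a non-significant result as evidence of safety.

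The cost is analysis-plan wording and a few tables. Dosing is already recorded, duration of blinded treatment is already to be summarised, and both blinded groups share one eye-examination schedule. No visit, procedure or treatment rule changes.
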